Inclusion Criteria	Exclusion Criteria
Confirmed COVID-19 +	Stage 3 AKI by KDIGO criteria
Admission to ICU or step-down units at WVU	CKD stage 4-5
Foley catheter* and central line (or PICC) in place	Contraindications to Na bicarbonate therapy (e.g. met. alkalosis, severe heart failure)
Age ≥ 18 y	Urine pH > 7.0
	ECMO Patients

*Foley Catheter can be removed 72 hours after enrollment if appropriate documentation of urine output can be maintained

Urine alkalinization may also increase the elimination of certain drugs including hydroxychloroquine. We do not intend to exclude patients taking these drugs but it will be discussed in the consent form and with the treating physicians.

Intervention: The intervention is a modification/simplification of a standard protocol used for decades for the treatment of various drug toxicities (e.g. salicylate) or to mitigate kidney damage from chemotherapy.[25] Simplifications are intended to tailor the intervention to the management of COVID-19 patients and reduce or eliminate any additional staff exposure. We will continue urine alkalinization for 10 days or until patient is discharged from ICU or step-down unit or until the stage 3 AKI or a safety endpoint is reached. Urine pH will be measured at POC by dipstick. The major elements of the interventional protocol are shown in Table 2. Note, much of the monitoring (e.g. blood gases, calcium) is already performed for routine care. The protocol simply ensures that these measurements are timed to maximize patient safety and minimize burden on bedside nurses. The protocol has been developed with input from [name], Professor and Vice Chair for Research in the Department of Critical Care Medicine at the University of Pittsburgh.

Table 2. Protocol highlights
Sodium bicarbonate 225 mmol (225 mL of an 8.4% solution) intravenously over 1h
Recheck urine pH (dipstick) in 2-4 hours (from start of infusion)
Repeat boluses of intravenous sodium bicarbonate to achieve urine pH ≥ 7.2
Monitor urine pH every 2-4 hours until target is reached and then q6-8 hours
Sodium bicarbonate 8.4% solution should not exceed 900 ml (4 boluses) in 24h
Monitor plasma sodium, potassium, calcium every 12 hours and Acid-base status at least every 24 hours (Note: Arterial pH should not be > 7.50 , or venous > 7.55)
Acetazolamide (Diamox) can be administered at physicians' discretion to control systemic alkalinization and to help avoid fluid accumulation.

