Avoid fluid accumulation. If urine output does not increase to compensate for the increased fluid (it will in most cases, especially if kidney is protected), Lasix or Diamox can be added.
*If fluid balance cannot be maintained within +1L in 24 hours – protocol will be halted and resumed only if either the fluid balance can be correct to within +500mL in 24 hours or if the primary team decides that the patient has clinically appropriate fluid balance.

Data

collection: Information will be collected about patient demographics – date of birth, age, sex, race, weight, height, co-morbidities including but not limited to diabetes, hypertension, heart failure, coronary artery disease, previous cardiac surgeries, chronic kidney disease, cancers. Given the long history and familiarity with urine alkalinization, potential adverse effects (e.g. metabolic alkalosis, hypocalcemia) are well known. Data about renal function (creatinine, urine output, daily ins and outs), basic metabolic panel, blood gas, home medications, medications given during hospital stay and chart review to identify any relevant complications will also be performed. The provider survey will be performed using an online survey instrument and a link will be emailed to the provider to complete.

Sample collection: We will collect urine samples (1 before, 1 at 24 hours and 1 at 48 hours) from initiation of the protocol. Urine samples will be collected, processed and stored in accordance

with EH&S requirements for COVID-19 samples. At a later date and using alternative funding, we plan to analyze these samples for additional biomarkers either at WVU or at partner institution(s) in that study.[26] These biomarkers measure the cellular stress in the kidney[27] and will be examined in an ancillary study. The samples will be stored initially at the laboratories in WVU and then shipped to partner institution(s) for further testing of urine biomarkers as detailed above.

Statistical analysis: Descriptive statistics will be used for reporting: continuous variables expressed as median and interquartile range while categorical variables as frequency and percentages. No imputation will be performed and missing data will be treated as missing.

Aim 1: To determine feasibility and safety of a pragmatic urine alkalinization protocol for the prevention of AKI

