Primary feasibility outcome will be the proportion of patients treated who achieve >50% of urine measurements pH \geq 7.2 over the duration of treatment. Following specific adverse events will be monitored – hypokalemia (K<3.0meq/L), hypocalcemia (Ca<7.6mg/dL when corrected for albumin), Hypernatremia (Na>155meq/L), Volume overload (gaining weight >10% from admission weight during the protocol time-period, need for positive pressure ventilation or intubation due to volume overload), arrhythmias due to hypokalemia or hypocalcemia. To assess safety and feasibility, summary statistics including frequency, mean, standard deviation, median and interquartile range will be provided as applicable. Baseline data will be summarized comparing treatment groups over time. Chi-square/t-test will be used to compare the difference between treatment groups. Mixed model /ANCOVA will be used for repeated measurements over time.

As per the requirements of COE, a Data Safety Monitoring Board (DSMB) has been established that includes [name] [name], [name], [name] and [name] [name]. The DSMB will meet to review any adverse events after 5 and 25 patients have been recruited. In addition, as per the requirements of COE, the DSMB will meet to review any adverse events after the first 5 patients randomized to the interventional drug (open label arm) have been recruited and completed the study.

Aim 2: To determine the efficacy of urine alkalinization for prevention of AKI

Primary efficacy outcome will be the number of days alive and free of stage 2-3 AKI (up to 28) in each group. Secondary endpoints will include the proportion of patients developing stage 2-3 AKI (or stage 3 if already at stage 2 at enrollment); ventilator-free days to 28 and hospital-free days to 60. For AKI-free, ventilator-free, and hospital-free days, zero truncated negative binomial models will be implemented.

Severe AKI will be considered as binary outcome. Multivariable logistic regression will be used to assess the overall odds associated with treatment adjusted by baseline covariates (age, demographics, baseline renal function). Random forest decision tree regression method will be implemented to assess patient variable importance towards the outcome. Hazard will be assessed using cox proportional hazard model.

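### The only calcium safety event is albumin-corrected calcium, which is insensitive to a pH-driven fall in ionized calcium; ionized calcium should be added as a reported outcome

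*Combined protocol and SAP*

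**What the plan says.** The Aim 1 part of the Statistical analysis (section 5, Approach) lists the specific adverse events to be monitored. For calcium the entry is "hypocalcemia (Ca<7.6mg/dL when corrected for albumin". A separate entry covers "arrhythmias due to hypokalemia or hypocalcemia". Ionized calcium is not mentioned anywhere in the document, and metabolic alkalosis is not on the Aim 1 list.

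The Data collection paragraph says of alkalinization that "potential adverse effects (e.g. metabolic alkalosis, hypocalcemia) are well known". It lists what will be gathered, including "basic metabolic panel, blood gas, home medications, medications given during hospital stay and chart review to identify any relevant complications". Albumin is not named there.

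Table 2, which describes the interventional protocol, says "Monitor plasma sodium, potassium, calcium every 12 hours and Acid-base status at least every 24 hours". It does not say whether calcium is total or ionized, and it does not list albumin. The same row gives a systemic limit: "Arterial pH should not be > 7.50 , or venous > 7.55".

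On missing values, the Statistical analysis paragraph says "No imputation will be performed and missing data will be treated as missing".

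**The concern.** The plan expects the infusion to push blood pH upward: it sets a pH limit and allows acetazolamide to control systemic alkalinization. By standard physiology, which the documents do not discuss, a higher blood pH makes more calcium bind to albumin. The ionized fraction falls while total calcium and albumin stay as they were. A measure built only from total calcium and albumin cannot pick up that part of the effect.

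Safety is half of Aim 1, the DSMB reviews adverse events, and 20 patients per group are planned. If the calcium event is insensitive to one of the routes by which this treatment acts, the arms can look more alike on calcium than they are. In so small a trial, few or no recorded events would be easy to read as reassurance.

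There is a smaller, separate gap. The event needs an albumin value, and albumin is not explicitly among the items to be collected.

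**Working it through.** **The plan's own figures.** The plan gives no calcium result to reproduce. Its one reproducible figure, 16 per group for Aim 2, comes back as 2 × (1.96 + 0.842)² × 5² / 5² = 15.7, so 16 (two-sided 0.05 and 80% power assumed). Nothing below affects it.

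**Inputs from the documents.** Event limit 7.6 mg/dL, albumin-corrected (Aim 1). Arterial pH limit 7.50 (Table 2). Calcium every 12 hours and acid-base status at least every 24 hours (Table 2). Treatment for up to 10 days (Intervention). 20 patients per group (Sample size determination).

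**Assumptions not in the documents.** Ionized calcium falls 0.03-0.08 mmol/L per 0.1 rise in pH. Starting pH is 7.35-7.40 and starting ionized calcium 1.15 mmol/L. Corrected calcium = total + 0.8 × (4.0 − albumin), in mg/dL and g/dL. A basic metabolic panel reports calcium without albumin.

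**Step 1: binding effect on each measure.** Fall in ionized calcium = slope × (pH rise / 0.1).

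| pH rise | Fall in ionized calcium (mmol/L) | Share of 1.15 | Change in corrected calcium from binding alone |
|---|---|---|---|
| 7.40 to 7.50 | 1.0 × 0.03 to 1.0 × 0.08 = 0.03 to 0.08 | 2.6% to 7.0% | 0 |
| 7.35 to 7.50 | 1.5 × 0.03 to 1.5 × 0.08 = 0.045 to 0.12 | 3.9% to 10.4% | 0 |

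The last column is zero because neither term of the correction formula changes. It describes the binding effect only. Dilution by the infusate, or urinary loss, can still lower total calcium and so the corrected value.

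**Step 2: role of albumin.** At albumin 2.5 g/dL the correction is 0.8 × (4.0 − 2.5) = 1.2 mg/dL. A measured 7.0 mg/dL is below 7.6 uncorrected, but corrects to 8.2 and is then not an event. A corrected 7.6 corresponds to a measured 7.2, 6.8, 6.4 or 6.0 mg/dL at albumin 3.5, 3.0, 2.5 or 2.0 g/dL. Over that albumin range, a measured total between 6.0 and 7.6 mg/dL cannot be classified without albumin, and the no-imputation rule leaves it missing.

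**Step 3: what incomplete capture does with 20 treated patients (illustration).** P(at least one event recorded) = 1 − (1 − rate × share captured)^20.

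| True event rate | All captured | Half | A quarter |
|---|---|---|---|
| 10% | 88% | 64% | 40% |
| 20% | 99% | 88% | 64% |

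The documents fix neither the rate nor the share captured. The table shows direction and sensitivity only.

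**Step 4: sampling.** Over 10 days, calcium every 12 hours gives 20 values per treated patient, while the acid-base minimum gives 10. Table 2 belongs to the intervention, and no blood-gas schedule is stated for standard care. Ionized calcium from gases may therefore be sparser than the present calcium measure and unequal between arms. The fix has to allow for this.

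**The case against.** The strongest reply is that the document names hypocalcemia as a known effect but gives no mechanism, so the slope, the starting values and the albumin correction all come from outside. That is true. The size is a range under stated assumptions, not a figure from the plan. The qualitative point needs only the accepted direction of the pH effect and a plan that expects blood pH to rise.

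Four stronger readings are tempting and are not supported:

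- *The event is blind to the drug.* It is insensitive to one route. The plan allows up to 900 mL of bicarbonate solution in 24 hours, and Lasix may be added, so total calcium can move by dilution or urinary loss.
- *A hypocalcemia event is shown to be missed.* A fall from 1.15 to about 1.03-1.12 mmol/L is not shown to cross any limit, and the larger falls assume that pH reaches the plan's ceiling.
- *The event cannot be computed.* Table 2 gives highlights, not a case-report form. The planned chart review could retrieve albumin, and a definition that corrects for albumin itself calls for it. What stands is missing detail: albumin is not listed, and handling of a calcium value without albumin is not stated.
- *The arrhythmia event depends on the same measure.* It is a separate entry, and its attribution is not tied to the 7.6 mg/dL criterion.

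There are also partial safeguards: blood gases are collected, pH is monitored and limited, and the DSMB reviews adverse events. These track the cause of the shift. They do not report its effect on ionized calcium by arm.

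The objection to replacing the event stands in full. Gas-based ionized calcium could halve the minimum sampling and give unequal detection in an open-label trial. It could also alter the unspecified safety endpoint at which the Intervention paragraph ends treatment.

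**Conclusion.** The point holds as a limited weakness in one safety measure. As written, the Aim 1 comparison can understate the treatment's effect on calcium, because its only laboratory criterion does not register increased protein binding at higher blood pH. Under the stated assumptions the unregistered fall in ionized calcium is about 0.03-0.12 mmol/L at the plan's pH limit, or 2.6-10.4% of an assumed 1.15 mmol/L. How much of the treatment's total effect on calcium goes unregistered cannot be derived from the documents. Calcium supplementation, which the open-label design allows, could hide further differences on either measure.

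The feasibility outcome, the sample size and the Aim 2 analyses are unaffected. A reader might infer that the calcium event is invalid or should be replaced. The documents do not support that. They support adding a measure and completing the data list: a cheap improvement.

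**What to change.** Keep the existing calcium event as it is and make these additions:

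1. Add ionized calcium, from the blood gases already collected, as a prespecified safety outcome in both arms. Report change from baseline and the proportion of patients below the local laboratory's reference limit.
2. Compare the arms at matched times, for example one value per patient per day chosen by a fixed rule, and report the number of measurements per arm. More frequent gases in the treated arm then do not create a detection difference.
3. Add albumin to the data list, name the calcium assay, and state how a calcium value without a same-day albumin is classified.
4. Leave every treatment-stopping rule unchanged. The investigators should state whether the calcium event is one of the safety endpoints mentioned under Intervention, which the document does not say.

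The cost is a paragraph of text and one or two case-report-form fields. The downside is missing values wherever a gas panel does not report ionized calcium, or where few gases are drawn. Those should be counted and reported by arm.

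### The volume-overload event is an insensitive measure of fluid accumulation: a patient halted for fluid balance need not count, and follow-up weights have no stated timing

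*Combined protocol and SAP*

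**What the plan says.** All references are to the combined protocol and SAP, section 5 (Approach).

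- **Event definition (Statistical analysis, Aim 1).** The listed adverse events include "Volume overload (gaining weight >10% from admission weight during the protocol time-period", with a second limb, "need for positive pressure ventilation or intubation due to volume overload". No other fluid criterion appears in the list.
- **Halt rule (end of Table 2).** "If fluid balance cannot be maintained within +1L in 24 hours", the protocol is halted. It may resume once the balance is back within +500 mL in 24 hours, or "if the primary team decides that the patient has clinically appropriate fluid balance". The line before it tells staff to prevent fluid build-up and allows a diuretic to be added.
- **Duration (Intervention).** "We will continue urine alkalinization for 10 days or until patient is discharged from ICU or step-down unit", or until stage 3 AKI or a safety endpoint.
- **Study fluid (Table 2).** "Sodium bicarbonate 8.4% solution should not exceed 900 ml (4 boluses) in 24h".
- **Data collection.** Weight appears once, in the baseline list: "date of birth, age, sex, race, weight, height, co-morbidities". Daily intake and output are collected, and charts are reviewed for complications.
- **Missing data (Statistical analysis).** Nothing is imputed.
- **DSMB (Aim 1).** The board reviews adverse events after 5 and 25 patients, and again after the first 5 patients randomized to the intervention have completed the study.

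**The concern.** Aim 1 is about feasibility and safety, and the hypothesis claims that alkalinization is safe. Fluid accumulation is the one harm for which Table 2 sets a numeric limit on balance tied to halting the protocol. Yet neither exceeding that limit nor being halted is a listed event, and no named safety outcome uses the daily intake and output.

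The two limbs of the event leave gaps. The weight limb needs at least one later weight, and no timing for one is given. The ventilation limb depends on judging that ventilation was needed because of overload. The Significance section says most patients present with severe hypoxemia, and the trial is open-label, so that attribution is difficult. A patient who is already ventilated may not trigger it at all.

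Followed as written, the plan could halt several of the 20 planned treated patients for fluid, some more than once, and still report no volume overload. The DSMB would not be assured of seeing those halts, and the safety conclusion would go into the planned pooling with the second center.

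**Working it through.** There is no derived figure in the plan to reproduce here, because both limits are set by design. The one related product checks: 4 boluses × 225 mL = 900 mL, the stated 24-hour cap.

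**Inputs from the documents:** event threshold above 10% of admission weight; halt limit +1 L in 24 hours; resumption figure +500 mL in 24 hours; course of at most 10 days.

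**Assumptions:** 1 L of retained fluid weighs 1 kg. The documents give no body weights, so a range of 50 to 150 kg is shown.

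**Formulas**, for weight W in kg and balance B in litres:
- weight-limb threshold = 0.10 × W
- gain from one day = 100 × B / W
- gain from 10 days at a constant daily balance = 100 × 10 × B / W

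| W (kg) | 10% threshold (kg) | One day at +1 L | One day at +2 L | 10 days at +1 L/day | 10 days at +0.5 L/day |
|---|---|---|---|---|---|
| 50 | 5 | 2.0% | 4.0% | 20.0% | 10.0% |
| 70 | 7 | 1.4% | 2.9% | 14.3% | 7.1% |
| 80 | 8 | 1.25% | 2.5% | 12.5% | 6.25% |
| 100 | 10 | 1.0% | 2.0% | 10.0% | 5.0% |
| 120 | 12 | 0.8% | 1.7% | 8.3% | 4.2% |
| 150 | 15 | 0.7% | 1.3% | 6.7% | 3.3% |

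**Step 1, a single breach.** A patient halted after one day at +1 to +2 L has gained 1.0 to 2.9% at 70 to 100 kg, and 0.7 to 4.0% over the whole range. That is below 10% throughout, so the breach alone does not produce an event on the weight limb.

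**Step 2, the same limits on a common time scale.** At exactly +1 L every day the halt limit is never exceeded. The gain passes 10% after day 5 at 50 kg, day 7 at 70 kg and day 8 at 80 kg. At 100 kg it equals 10% on day 10 and so does not exceed it. Above 100 kg it stays below. At +0.5 L/day, only patients under 50 kg pass 10% in 10 days.

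**Step 3, whether the weight limb can be assessed.** It needs an admission weight and at least one later weight. Table 2 gives timings for urine pH, electrolytes and acid-base status, but none for weight, and the data-collection text gives no repeat schedule. With no imputation, a patient without a later weight cannot be assessed on this limb.

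**The case against.** The strongest reply is that a halt trigger and an adverse-event definition do different jobs. The trigger acts before harm and the event records harm, so setting the trigger lower is sensible. One is also a 24-hour limit and the other a cumulative gain. That stands.

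A reader might infer three stronger points, and the documents support none of them.

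- **That the two limits conflict, or that the event cannot be reached under the halt rule.** Step 2 shows that patients under 100 kg can pass 10% within 10 days without a breach. Nor is the halt rule a ceiling on weight gain: it stops the study protocol, nothing says it stops other fluids, and the primary team's judgement can lift it. Controls have no halt rule.
- **That fluid harm goes unrecorded.** Daily intake and output, hospital medications and chart review all record relevant information, and the ventilation limb needs no weights. Protocol adherence is also an Aim 1 outcome, where halts might appear.
- **That follow-up weights are not taken.** Saying that weight gain will be monitored implies some later weights, and Table 2 presents highlights, not a full schedule. What can be said is that no timing is given.

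These routes do not close the gap. Chart review has no fluid criterion, adherence is not defined and is not a safety measure, and none of them commits the plan to comparing fluid accumulation between arms.

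**Conclusion.** The point holds as one of measurement and reporting. The plan can record fluid accumulation without classifying it as volume overload or comparing it between arms. A fluid halt can occur at about 1 to 3% of body weight, against an event threshold above 10%, and need not be counted anywhere in the safety results. The number of patients assessable on the weight limb is not fixed by the plan.

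The size rests on taking 1 L as 1 kg and on assumed body weights. The documents give no expected frequency of halts, so the number of uncounted patients cannot be estimated. The finding does not show that the 10% threshold or the halt rule is wrong. It is a worthwhile, low-cost improvement to the safety reporting of a 40-patient trial, and does not invalidate the design.

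**What to change.** Keep the event definition as it stands, without regrading the weight limb as a severe category, and add the following to the Aim 1 safety analysis.

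1. **Both arms, from the daily intake and output:** (a) cumulative fluid balance from randomization to day 10 or the end of the ICU or step-down stay, continuing through any halt; (b) the number of days with a 24-hour balance above the plan's own +1 L limit. Report these descriptively, with the number of days observed, and not as adverse events.
2. **Treated arm:** record and report the number of patients and occasions halted, and resumed, for fluid balance. Give these counts to the DSMB at its planned reviews.
3. **Weights:** state when follow-up weights are taken, with the same timing in both arms, and report how many patients per arm can be assessed on the weight limb.
4. **Text:** the investigators should reconcile the Table 2 limit with the Aim 1 definition by saying how a fluid halt relates to the volume-overload event. No change to the halt rule or to any clinical threshold is proposed.

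The cost is small. Item 1 uses data already collected. Item 2 needs a halt and resumption entry, which the data-collection text does not list, and item 3 needs a weight schedule. The downside is that days above +1 L are likely to be common among ICU patients in both arms (an assumption, as the documents give no rate). They are therefore non-specific and should be read as a comparison between arms.

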Thus, the innovative idea of simply drinking sodium bicarbonate solutions to induce minor changes in blood pH has been proposed.[21] This idea suffers from two major limitations. First, the pH change required to have significant effect on disrupting the RBD is likely to be too great to safely achieve in blood—a rule of thumb is at least 1 pH unit.[23] Second, even if this could be achieved the expression of ACEr is on the apical (lumen) surface of epithelial cells not the basolateral (plasma) side.[16] However, neither of these are problems for the kidney. Urine pH

is normally 5.5-6.5 (not too dissimilar to alveolar fluid—6.4-6.8[24]) and can be easily and safely manipulated. In fact, urine alkalinization protocols have been used for decades to reduce renal toxicity from various compounds (especially chemotherapy) and are recommended by US and European toxicology societies.[25] Here, the strategy will be deployed not for ion trapping but to inhibit the virus from infecting RTEC. Alkalizing the urine using IV sodium-bicarbonate solution to pH of 7.5 or more can be easily and safely achieved. Acetazolamide can also be added if systemic alkalemia is an issue.[25] An additional advantage of this approach is that it is unlikely to interfere with other interventions that can be studied in these patients (e.g. steroids) which are directed at the lungs.

5. Approach

We will conduct a pragmatic RCT using alkalinization of urine such that most ICU COVID-19 positive patients can be enrolled. Both specific aims will be achieved by the conduct of the trial yet both are independent. The statistical analysis plan for each aim will detail the specific endpoints and hypotheses being testing.

Trial overview: Study inclusion and exclusion criteria are provided in Table 1.

Study design: Open-label randomized trial (1:1) comparing urine alkalinization to standard care. The study will test both feasibility and safety (aim 1) as well as efficacy (aim 2).

Study Management: Study personnel will identify patients and obtain video-enabled informed consent from patients or legally authorized representatives; collect study data and ensure sample collection, processing and storage. The patient's bedside nurse will perform urine pH measurement (dipstick) and deliver the study drug. The study is open-label to facilitate safety and allow for any management of complications (e.g. calcium supplementation).

Table 1. Inclusion/exclusion Criteria

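### Two of the six adverse-event criteria count only after a causal judgement, with no attribution rule, named assessor or masking in an open-label trial, so the between-arm comparison of those two rows is open to assessor bias.

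*Combined protocol and SAP*

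**What the plan says.** The Aim 1 paragraph under Statistical analysis (section 5, Approach) lists the adverse events to be monitored. Four criteria have a numeric cut-off: three laboratory values, "hypokalemia (K<3.0meq/L), hypocalcemia (Ca<7.6mg/dL when corrected for albumin), Hypernatremia (Na>155meq/L", and one limb of volume overload, "gaining weight >10% from admission weight during the protocol time-period". The other two carry a causal qualifier. The second limb of volume overload is "need for positive pressure ventilation or intubation due to volume overload", and the last item is "arrhythmias due to hypokalemia or hypocalcemia".

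Study design describes an "Open-label randomized trial (1:1) comparing urine alkalinization to standard care". Study Management gives the reason: "The study is open-label to facilitate safety and allow for any management of complications". Data collection states that "chart review to identify any relevant complications will also be performed". The Aim 1 paragraph goes on to promise summary statistics for safety and feasibility, and mentions chi-square and t-tests between groups. The DSMB is to review adverse events at set points in recruitment.

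For the two qualified items the documents give no time window, no requirement for a concurrent laboratory value, no ECG criterion, no named assessor and no masked adjudication.

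**The concern.** Safety is half of the stated hypothesis (section 2) and part of Aim 1, so the adverse-event table is a main product of the trial. Arrhythmia and ventilation are clinical events, and each enters its row only if someone decides what caused it.

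For ventilation there is a strong competing cause in both arms. Section 3 says most patients present with severe hypoxemia. Whether an intubation was caused by fluid or by lung disease is a matter of judgement, and knowing that a patient received bicarbonate boluses can influence it. Suspicion of the intervention would raise the treated count. Confidence in its safety, which the protocol expresses more than once, would lower it. Either can happen with no true difference, and either can hide a true one.

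The arrhythmia row is also narrow. Data collection names metabolic alkalosis as a known adverse effect, and Table 2 sets a ceiling on blood pH. Yet an arrhythmia attributed to alkalosis, or to hypernatremia, does not meet the listed definition.

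**Working it through.** **Inputs.** Planned size is 20 per arm, 40 in total (Sample size determination). The documents give no event rates and no attribution shares, so those used below are assumptions.

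**The plan's own figure.** No stated figure bears directly on this point. The one reproducible design figure is the 16 per group for efficacy: n = 2 × (1.960 + 0.842)² × 5² / 5² = 15.7, rounded up to 16. This assumes two-sided alpha of 0.05 and 80% power, neither of which is stated. It matters here only as background to the 20 per arm.

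**Step 1: sort the criteria.**

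| Criterion | Decided by |
|---|---|
| Potassium | numeric cut-off |
| Corrected calcium | numeric cut-off |
| Sodium | numeric cut-off |
| Weight gain | numeric cut-off |
| Ventilation or intubation | attribution to volume overload |
| Arrhythmia | attribution to low potassium or calcium |

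Four of six need no causal judgement; two do.

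**Step 2: equal true rates.** Expected listed count = 20 × true rate × share attributed.

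| True rate, both arms | All events counted | 50% vs 25% attributed | 75% vs 25% attributed | 25% vs 50% attributed |
|---|---|---|---|---|
| 10% | 2 vs 2 | 1 vs 0.5 | 1.5 vs 0.5 | 0.5 vs 1 |
| 20% | 4 vs 4 | 2 vs 1 | 3 vs 1 | 1 vs 2 |
| 40% | 8 vs 8 | 4 vs 2 | 6 vs 2 | 2 vs 4 |
| Ratio | 1.0 | 2.0 | 3.0 | 0.5 |

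The apparent ratio equals the ratio of the attribution shares, whatever the true rate. If the shares are equal in the two arms, the ratio is undistorted.

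**Step 3: a true difference hidden.** Take true rates of 40% and 20%, so 20 × 0.40 = 8 and 20 × 0.20 = 4 events. Attributed at 25% and 50%, the table shows 8 × 0.25 = 2 and 4 × 0.50 = 2. A true doubling disappears.

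**Step 4: how few classifications matter with 20 per arm.**

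| Listed counts | Chi-square p (uncorrected) | Fisher p |
|---|---|---|
| 3 vs 3 | 1.00 | 1.00 |
| 3 vs 1 | 0.29 | 0.60 |
| 5 vs 1 | 0.08 | 0.18 |
| 6 vs 1 | 0.04 | 0.09 |

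Most plausible distortions would not reach significance. They would change the descriptive picture, which is what readers and the DSMB will use in a trial of 40.

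**Step 5: what counting all events gains.** The true 8 vs 4 would be shown as 8 vs 4. The uncorrected chi-square is 40 × (8 × 16 − 12 × 4)² / (20 × 20 × 12 × 28) = 1.90, p about 0.17. The gain is an estimate free of attribution bias, not power.

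**The case against.** The case on the other side has real content.

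- **Only part of the list is affected.** A reader might infer that the whole safety comparison rests on opinion about the drug. The documents do not support that. Four of six criteria are numeric, volume overload can be met on weight alone, and the judgement asked for concerns electrolytes or fluid rather than the drug. This stands.
- **Ventilation is already compared without a causal qualifier.** Ventilator-free days to 28 is a secondary endpoint under Aim 2. It would therefore be wrong to infer that the randomised comparison is lost for ventilation. That endpoint is indirect, though: it is not a count of new events and may not capture non-invasive support.
- **Other arrhythmias are not said to go unrecorded.** Chart review covers relevant complications, blood gases are collected, and the DSMB reviews any adverse events. What the text supports is that an arrhythmia from another cause falls outside the listed row. No masked or classifying role is given to the DSMB, so its review does not settle the attribution.
- **The assessor is not named.** That the judgement is made by people who know the arm is a fair inference from the open-label design, not a documented fact.
- **Arrhythmia attribution is partly anchored.** Low potassium and low calcium have cut-offs in the same sentence, and the natural reading is that a qualifying value is needed. The text does not say so and gives no time window, so the gap is narrowed but not closed.
- **Formal testing is uncertain.** Safety is assigned summary statistics, and the chi-square sentence directly follows one about baseline data. It is unclear that adverse events will be tested at all. A descriptive table by arm is biased in the same way.
- **The shares are assumed.** This stands; the working shows a range, not an estimate.

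**Conclusion.** The point holds for two rows of the adverse-event list. Arrhythmia and ventilation or intubation are counted only after a causal judgement, in an open-label trial with no stated rule, assessor or masking, so their comparison between arms is open to bias of unknown direction. The four numeric criteria are unaffected by this problem, and ventilator-free days offers a partial check on ventilation.

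The size cannot be estimated from the documents. Under the assumed shares, the listed ratio runs from 0.5 to 3.0 when the true ratio is 1.0, and a true doubling can vanish. This rests on two assumptions: that whoever attributes cause knows the arm, and that this knowledge shifts the share attributed. If attribution were equal in the two arms, the comparison would be thinned but not biased.

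This is a worthwhile, low-cost improvement to the safety analysis. It does not invalidate the safety assessment as a whole.

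**What to change.** In the Aim 1 analysis, tabulate and compare the following by randomised arm, over the same fixed window from randomisation in both arms (for example through day 10, the maximum length of the intervention):

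- all new arrhythmias, regardless of cause;
- all new positive-pressure ventilation or intubation, regardless of cause, with patients not already ventilated at randomisation as the denominator. Table 1 does not exclude patients who are already ventilated, so the denominator must be stated.

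Keep the attributed counts as a descriptive sub-row under each. A pre-specified attribution rule, preferably applied by a masked assessor, would make that sub-row more useful, but the main comparison would not depend on it.

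**Cost.** The change is mostly wording, because chart review is already planned and ventilation data are needed for ventilator-free days. Chart abstraction must, however, capture every new arrhythmia in both arms, not only those thought relevant. Background COVID-19 events will add noise in both arms and, with 20 per arm, may obscure a modest signal. Clinicians who know the arm still decide on ventilation, so open-label influence is reduced but not removed.
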